#### Elevation of Either ALT or AST to $\geq 3 \times$ ULN

Confirmation is required prior to IMP discontinuation in cases of elevation of either ALT or AST  $\geq 3 \times$  ULN (Note: In cases of elevation of ALT or AST  $\geq 8 \times$  the ULN, no confirmation is required prior to IMP discontinuation, but the assessments below should be performed). The following procedures should be followed:

- The day in which the abnormal value is received from the laboratory will be considered as day 0.
- The Investigator should repeat the test for confirmation purposes (this may be performed in a local laboratory along with complete blood count [CBC] and differential to assess for eosinophilia. In general, in case a blood sample is sent to a local laboratory, the following assessments [and reference ranges] are mandatory: ALT [serum glutamic pyruvic transaminase], AST [serum glutamic oxaloacetic transaminase], ALP, total bilirubin, CBC [with differential for eosinophil count, separate tube], and INR [separate tube; not to be sent in a confirmatory test]). The Investigator should also question the participant regarding symptoms.

---

 In case total bilirubin is  $>$ ULN, then direct bilirubin will be checked.

 Thorough medical history with a focus on liver disease: personal or family history of liver disease; personal history of a systemic disease with potential liver involvement; exposure to alcohol, medications (prescription or over the counter), herbal preparations, dietary supplements, recreational drugs, special diets, or environmental chemical agents; potential exposure to infectious agents (eg, travel to developing countries, history of potential exposure to blood or blood products, high-risk sexual relations); and any additional information deemed relevant by the Investigator. Physical examination, including signs of chronic liver disease.

The abnormality will be regarded as confirmed in each of the following scenarios:

- the baseline value was within the normal range and ALT or AST is still  $\geq 3 \times$  the ULN
- the baseline value was above the ULN and ALT or AST is  $\geq 2 \times$  the baseline value

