## 7. DISCONTINUATION OF TRIAL INTERVENTION AND PARTICIPANT WITHDRAWAL FROM TRIAL

### 7.1. Discontinuation of Trial Intervention

In the following circumstances for participant with abnormal hepatic laboratory values (eg, ALT, AST, ALP, gamma-glutamyl transpeptidase, total bilirubin, or International Normalized Ratio [INR]), IMP should be discontinued immediately:

1. any increase in ALT or AST to  $\geq 3 \times$  the ULN, combined with INR  $> 1.5 \times$  the ULN or total bilirubin  $\geq 2 \times$  the ULN
2. any increase in ALT or AST to  $\geq 3 \times$  the ULN, which is accompanied by symptoms clearly associated with impaired liver function (eg, vomiting, nausea, fever, rash, or eosinophilia) and not deemed related to other diseases (eg, vomiting or nausea triggered by migraine)
3. any increase in ALT or AST to levels  $\geq 5$  but  $< 8 \times$  the ULN, which is persistent for  $\geq 2$  weeks of repeated measurements
4. any increase in ALT or AST to levels  $\geq 8 \times$  the ULN
5. in any case where monitoring of liver enzymes cannot be performed according to the protocol guidance

The participant must be withdrawn from the IMP if the participant experiences a severe hypersensitivity reaction or anaphylaxis.

Additionally, IMP should be discontinued if the participant experiences an adverse event or other medical condition indicating to the Investigator that continued participation is not in the best interest of the participant.

A participant who is randomized/enrolled but does not complete the treatment period will not be replaced (see Section 9.8).

All protocol-specified procedures/assessments should be performed at the EOT/early withdrawal visit (see Table 1).

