**Stopping Rules**

In the following circumstances, the IMP will be discontinued immediately:

- any increase in ALT or AST to  $\geq 3 \times$  the ULN, combined with INR  $>1.5 \times$  the ULN or total bilirubin  $>2 \times$  the ULN
- any increase in ALT or AST to  $\geq 3 \times$  the ULN, which is accompanied by symptoms clearly associated with impaired liver function (eg, vomiting, nausea, fever, rash, eosinophilia) and not deemed related to other diseases (eg, vomiting or nausea triggered by migraine)
- any increase in ALT or AST to levels  $\geq 5$  but  $<8 \times$  the ULN, which is persistent for  $\geq 2$  weeks of repeated measurements
- any increase in ALT or AST to levels  $\geq 8 \times$  the ULN
- in any case where monitoring of liver enzymes cannot be performed according to the protocol guidance

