8.4. Adverse Events

All adverse events will be coded using the Medical Dictionary for Regulatory Activities (MedDRA).

For adverse event recording, the trial period is defined for each participant as the time period from signature of the informed consent form through completion of visit 5 or the early withdrawal visit for participants who withdraw from the trial for any reason.

Adverse events will be collected at each visit via adverse event inquiry.

The following are considered protocol-defined adverse events of special interest to be sent to the Sponsor's Pharmacovigilance Department for evaluation: ophthalmic related adverse events of at least moderate severity and severe hypersensitivity or anaphylactic reactions.

An adverse device effect is an adverse event related to the use of an investigational medical device or combination product. The full definition is provided in the trial protocol.

Events of possible drug-induced liver injury (AST or ALT $\geq 3 \times$ the ULN, total bilirubin $\geq 2 \times$ the ULN), or Hy's Law events, as well anaphylaxis and hypersensitivity reactions will be assessed. Hypersensitivity reactions will be monitored using the diagnostic criteria for anaphylaxis as

outlined by the 2006 Joint National Institute of Allergy and Infectious Disease/Food Allergy and Anaphylaxis Network Second Symposium on Anaphylaxis ([Sampson et al, 2006](#)). In the event of suspected anaphylaxis, vital signs, including oxygen saturation and respiration rate, will be measured.

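### For ALT or AST from 3 to below 8 times ULN with raised INR, raised bilirubin or liver symptoms, the protocol asks both for a confirmatory repeat before stopping IMP and for an immediate stop

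*Protocol*

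**What the plan says.** Three places in the protocol deal with stopping IMP for liver enzymes.

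- **Protocol 12.2.1, on elevations to at least 3 times ULN.** "Confirmation is required prior to IMP discontinuation in cases of elevation of either ALT or AST" at or above 3 times ULN. The one exception is at or above 8 times ULN, where "no confirmation is required prior to IMP discontinuation, but the assessments below should be performed". For the rest, "The Investigator should repeat the test for confirmation purposes". INR is marked as "not to be sent in a confirmatory test". The rise counts as confirmed if baseline was normal and ALT or AST is still at least 3 times ULN, or if baseline was above ULN and the value is at least twice baseline.
- **Protocol 12.2.1, Stopping Rules.** "In the following circumstances, the IMP will be discontinued immediately", followed by five circumstances. The first is ALT or AST of at least 3 times ULN with INR above 1.5 times ULN or total bilirubin strictly above 2 times ULN. The second is at least 3 times ULN with symptoms of impaired liver function.
- **Protocol 7.1.** "IMP should be discontinued immediately", followed by the same five circumstances, except that the bilirubin limit reads "total bilirubin $\geq 2 \times$ the ULN".

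Neither stopping list mentions confirmation or refers back to the confirmation step.

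**The concern.** A participant with ALT of, say, 3 times ULN and a qualifying INR, bilirubin or symptom finding meets a criterion for an immediate stop in two places and falls under a confirm-before-stopping instruction in a third. A site that waits for the repeat departs from 7.1 and from the Stopping Rules. A site that stops at once departs from the confirmation text.

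This is a safety decision rule in participants aged 6 to 17, in a trial without a data monitoring committee (Protocol 4.1.2), so sites should not have to choose between passages. The choice also reaches the data. Meeting a stopping rule brings early-withdrawal activities and at least 30 days of follow-up with weekly enzymes (Protocol 12.2.1). A participant who leaves the trial early counts as a non-responder (SAP 6.3.1.1), drops out of the per-protocol set, which requires completion (SAP 3.4), and enters the tolerability count of non-completers (SAP 9). Noncompliance with IMP administration can be an important protocol deviation (Protocol 11.2), so what is recorded as a deviation may depend on which passage is read.

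**Working it through.** No figure in the plan needs reproducing. The check sets the passages side by side, circumstance by circumstance.

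| ALT/AST circumstance | Confirmation text (12.2.1) | Stopping lists (7.1 and 12.2.1) | Result |
|---|---|---|---|
| 3 to below 8 × ULN with INR or bilirubin criterion | Repeat first | Stop at once | Conflict |
| 3 to below 8 × ULN with liver symptoms | Repeat first | Stop at once | Conflict |
| 5 to below 8 × ULN lasting at least 2 weeks | Repeat first | Stop; repeats are part of the criterion | No real conflict |
| At least 8 × ULN | Exempt | Stop at once | Agree |
| Monitoring not possible | Presupposes a repeat test | Stop at once | Awkward fit |
| Isolated rise, 3 to below 5 × ULN | Repeat | Not listed; monitored | No conflict |

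**INR.** Confirmation is defined on ALT or AST alone, and INR is left out of the confirmatory sample. A repeat therefore cannot confirm the INR part of the first criterion.

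**Bilirubin.** Let b be total bilirubin divided by ULN. Section 7.1 is met when b ≥ 2; the 12.2.1 rule is met when b > 2. Below 2 neither is met, and above 2 both are. They differ only at b = 2.0.

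**Timing.** IMP is given at visits 2, 3 and 4 (days 1, 29 and 57). Liver enzymes are scheduled at visits 1, 3 and 5. Visit 1 precedes dosing and visit 5 follows the last dose, so the visit 3 sample is the only scheduled one taken on treatment whose result can affect a later dose, and that dose is due 57 − 29 = 28 days later. Unscheduled tests are possible, but the dosing interval is the same. The protocol gives no deadline for the confirmatory repeat. If it is done within those 28 days, the two readings lead to the same next-dose decision whenever the rise is confirmed. They part when the repeat falls below the confirmation threshold: one reading has already stopped IMP, and the other has no confirmed rise on which to stop.

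**The case against.** The strongest defence is that 12.2.1 is one algorithm read in order: repeat the test, evaluate further, monitor by band, then apply the stopping rules. On that view *immediately* means without delay once the rise is confirmed. The defence has some force, because below 8 times ULN the confirmation sentence has little to govern apart from the combined criteria.

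It does not settle the matter. No passage states this sequence, and 7.1 does not refer to the confirmation step. The same word introduces all five circumstances, including at least 8 times ULN, where confirmation is expressly waived. It would have to mean *without confirmation* in one bullet and *after confirmation* in another. The exclusion of INR from the confirmatory sample strains the reading further.

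Two parts of the defence stand. Monthly dosing usually leaves room for a repeat, so the practical effect is small. The bilirubin difference is editorial.

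A reader might also take SAP 8.4 as a third version of the stopping rule, since it lists "Events of possible drug-induced liver injury" with bilirubin at or above 2 times ULN. The documents do not support that. SAP 8.4 defines events to be assessed and reported; it has no INR or symptom arm and no instruction to discontinue. It is not evidence of the conflict.

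**Conclusion.** The inconsistency is real and in the current protocol text, but it is confined to ALT or AST from 3 to below 8 times ULN combined with the INR, bilirubin or symptom criteria. A reader might infer that the passages clash for every rise of at least 3 times ULN. They do not: isolated rises from 3 to below 5 times ULN are monitored, the rule for 5 to below 8 times ULN has repeats built in, and the passages agree from 8 times ULN upward. The bilirubin operator is a side point that bites only at exactly 2.0 times ULN.

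The number of qualifying cases cannot be derived from the documents, and nothing in them shows an effect on the primary result. The view that the practical effect is limited assumes that a repeat is done before the next dose falls due. This review takes no position on which confirmation rule or bilirubin cut-off is right.

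**What to change.** Reconcile Protocol 7.1, the confirmation text in 12.2.1 and the Stopping Rules in 12.2.1, so that all three state one confirmation requirement for the combined criteria and one bilirubin operator, with a cross-reference between 7.1 and 12.2.1. SAP 8.4 need not change on this account. The cost is wording only, through an amendment or administrative letter.

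The note to file at the end of the SAP, dated 29 May 2025, says that the trial analysis was conducted, so dosing may have ended. In that case new protocol wording would no longer guide sites. The sponsor should instead check for participants who met the combined criteria and state in the CSR which reading was applied to each, or that there were none.

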### **Additional Tests/Evaluations**

Upon confirmation of the abnormality as noted above, the following additional evaluations should be performed and results should be recorded in the CRF:

- serology for hepatitis A (antibody and immunoglobulins M and G), B (core antibody total, core immunoglobulin M, and surface antigen), and C viruses (central laboratory)
- serology for autoimmune hepatitis: anti-nuclear antibodies (titer), anti-smooth muscle antibodies, and anti-liver kidney microsomal antibodies (central laboratory); further testing may be required in case of a positive result for hepatitis B or C
- ultrasound examination of the liver and biliary tract at the Investigator's discretion
- other diagnostic tests/consultations as deemed necessary by the Investigator (eg, serology for hepatitis E virus in case of travel to endemic geography)
- observation and follow-up (to be performed after the abnormality was confirmed as above)

### **ALT or AST $\geq 3 \times$ ( $>3.5 \times$ the ULN if the Baseline Value Is $>2.5 \times$ the ULN) but Less Than $5 \times$ the ULN**

In addition to the above procedures required for any elevation to levels  $>3 \times$  the ULN:

- ALT, AST, GGT, ALP, total and direct bilirubin, CBC and differential (to assess for eosinophilia), and INR should be monitored on days 5 ( $\pm 2$  days), 8 ( $\pm 2$  days), 14 ( $\pm 3$  days), and 28 ( $\pm 3$  days). On at least 1 of these days, the test should be performed centrally. (The INR should be sent to a local laboratory only.)
- In cases where a local laboratory is used, the results should be recorded in the CRF, accompanied by the reference range of the relevant measurements.
- Should the abnormality ( $\geq 3 \times$  the ULN in case baseline was within the normal range or  $\geq 2 \times$  the ULN in case the baseline value was above ULN but still  $<5 \times$  the ULN) persist further, the participant will be followed according to the Investigator's discretion, but a blood sample for ALT, AST, GGT, ALP, and total and direct bilirubin should be sent to the central laboratory at least once a month.

### **ALT or AST $\geq 5 \times$ but Less Than $8 \times$ the ULN**

In addition to the above procedures required for any elevation to levels  $>3 \times$  the ULN:

- ALT, AST, GGT, ALP, total and direct bilirubin, CBC and differential count (to assess for eosinophilia), and INR should be monitored twice a week.
- At least for every other measurement, the tests should be sent to the central laboratory. The rest of the tests may be sent to a local laboratory. The INR should always be sent to a local laboratory.

**ALT or AST  $\geq 8 \times$  the ULN**

In addition to the above procedures required for any elevation to levels  $>3 \times$  the ULN:

- The IMP should be discontinued immediately, and the early withdrawal visit should be performed.
- For follow-up guidance, please see below section “Follow-Up of Liver Enzymes After Stopping Rules Are Met.”

**Stopping Rules**

In the following circumstances, the IMP will be discontinued immediately:

- any increase in ALT or AST to  $\geq 3 \times$  the ULN, combined with INR  $>1.5 \times$  the ULN or total bilirubin  $>2 \times$  the ULN
- any increase in ALT or AST to  $\geq 3 \times$  the ULN, which is accompanied by symptoms clearly associated with impaired liver function (eg, vomiting, nausea, fever, rash, eosinophilia) and not deemed related to other diseases (eg, vomiting or nausea triggered by migraine)
- any increase in ALT or AST to levels  $\geq 5$  but  $<8 \times$  the ULN, which is persistent for  $\geq 2$  weeks of repeated measurements
- any increase in ALT or AST to levels  $\geq 8 \times$  the ULN
- in any case where monitoring of liver enzymes cannot be performed according to the protocol guidance

**Follow-Up of Liver Enzymes After Stopping Rules Are Met**

- A participant who meets the above criteria for discontinuation of the IMP should be invited to the site to return the IMP. Early withdrawal visit activities should be performed as soon as possible.
- Liver enzymes should be monitored until normalization or stabilization of the abnormality, according to the discretion of the Investigator.
- In any case, following the early withdrawal visit, the minimal follow-up period will be 30 days and will include measurement of liver enzymes at least once weekly (may be performed in local laboratory, with at least 1 test being sent to the central laboratory).
- Every effort should be made to complete the additional tests/evaluations, as described above.
- Every effort should be made to ensure that the participant continues to receive ongoing evaluation and treatment by their primary care physician after withdrawal from the trial.

## **13. APPENDIX: DEFINITIONS AND SUPPORTING OPERATIONAL DETAILS**

### **13.1. Contraception and Pregnancy Testing**

#### **13.1.1. Definitions Related to Childbearing Potential**

**Females of childbearing potential are defined as the following:**

- not surgically (documented hysterectomy, bilateral oophorectomy, or bilateral salpingectomy) or congenitally sterile
- postmenarchal or  $\geq 12$  years of age

**Females who are not of childbearing potential are defined as the following:**

- premenarchal and  $< 12$  years of age

#### **13.1.2. Contraception**

##### **Description of different birth control methods**

###### **Highly effective birth control methods:**

Highly effective birth control methods are methods that can achieve a failure rate of less than 1% per year when used consistently and correctly are considered. Such methods include the following:

- Progestogen-only hormonal contraception (oral, injectable, and implantable) associated with inhibition of ovulation; these should be initiated at least 1 month before the first dose of IMP
- Progestin and estrogen contraceptives (oral only) associated with inhibition of ovulation; these should be initiated at least 1 month before the first dose of IMP
- Intrauterine device and intrauterine hormone-releasing system need to be in place at least 2 months before screening
- Bilateral tubal occlusion
- Vasectomized partner, provided that he is the sole sexual partner and has received medical assessment of the surgical process
- Sexual abstinence is only considered a highly effective method if defined as refraining from heterosexual intercourse in the defined period. The reliability of sexual abstinence needs to be evaluated in relation to the duration of the clinical trial and the preferred and usual lifestyle of the participant.

###### **Unacceptable birth control methods:**

Periodic abstinence (calendar, symptothermal, and post-ovulation methods), withdrawal (coitus interruptus), spermicides only, and lactational amenorrhea method are not acceptable methods of contraception. Female condom and male condom should not be used together.

## Male contraception

Male participants who are sexually active with female partners must always use a condom for the duration of the trial and for 6 months after the last administration of IMP.

### 13.1.3. Pregnancy Testing

Beta-human chorionic gonadotropin ( $\beta$ -HCG) tests in serum or urine will be performed for all woman of childbearing potential at the time points as specified in [Table 1](#) and, if clinically indicated, thereafter:

- Refer to Section [5.3](#) for pregnancy testing inclusion criteria.
- Additional pregnancy tests (HCG in urine or serum) may be performed, as determined necessary by the Investigator or required by local regulation, to establish the absence of pregnancy at any time during the participant's participation in the trial.

## 13.2. Clinical Laboratory Tests

**Table 7: Clinical Laboratory Tests**

Serum chemistry	Hematology and coagulation	Urinalysis
Calcium	Hemoglobin	Color and appearance
Phosphate	Hematocrit	Protein
Sodium	RBC count	Glucose
Potassium	RBC indices	Ketones
Chloride	– mean corpuscular volume	Blood
Creatinine	– mean corpuscular hemoglobin concentration	Leukocyte esterase
Glucose	– RBC distribution width	Nitrite
BUN	Platelets	Bilirubin
ALT	Leukocytes	pH
AST	– neutrophils	Specific gravity
LDH	– lymphocytes	Microscopic tests
GGT	– eosinophils	– bacteria
Alkaline phosphatase	– monocytes	– erythrocytes
Creatine phosphokinase	– basophils	– leukocytes
Carbon dioxide	Prothrombin time	– crystals
Magnesium	Partial thromboplastin time	– casts
Protein	INR	
Albumin		
Bilirubin (total and direct)		

ALT=alanine aminotransferase; AST=aspartate aminotransferase; BUN=blood urea nitrogen; GGT=gamma-glutamyl transpeptidase; INR=International Normalized Ratio; LDH=lactate dehydrogenase; RBC=red blood cell.

### 13.3. Prior Protocol Amendments

#### Administrative Letter 06 Dated 21 December 2021

#### ADMINISTRATIVE LETTER 06

Study number: TV48125-CNS-30082

Clinical Study Protocol with Amendment 08

A Multicenter, Randomized, Double-Blind, Placebo-Controlled, Parallel-Group Study  
Comparing the Efficacy, Safety, and Tolerability of Subcutaneous Administration of  
Fremanezumab Versus Placebo for the Preventive Treatment of Chronic Migraine in Pediatric  
Patients 6 to 17 Years of Age, approved date 09 December 2021

IND number: 106,533; BLA number: 761089; EudraCT number: 2019-002053-33

21 December 2021

Dear Investigator:

The purpose of this letter is to correct inconsistencies and/or provide clarification for the protocol sections outlined below. Where applicable, changes made to the text (in italics) are shown (revisions and additions are shown in bold; deletions are in strikethrough).

In Section 3.5. Schedule of Study Procedures and Assessments, it is clarified that the date of the next dosing visit is always calculated based on the actual date of the last investigational medicinal product administration; regardless of whether the visit is out-of-window or not. Calculations, however, already account for this via the Interactive Response Technology System. Therefore, footnote "d", under the table of Study Procedures and Assessments (Table 1), is revised as shown in the table below.

Before	After
In case of an out-of-window visit, the date of the next visit will be calculated based on the actual date of the last administration of study drug.	In case of an out of window visit, <del>+The date of the next visit will be calculated based on the actual date of the last administration of study drug.</del>

In Section 7.4.2.1., the word "other" will be deleted from the sentence (as shown in the table below) in order to correct the discrepancy with pregnancy tests. Thus, clarifying that urine pregnancy tests are performed at all visits. The table of Study Procedures and Assessments (Table 1), however, correctly reflects the intent of the protocol, which is to perform urine pregnancy tests at all visits and serum beta-human chorionic gonadotropin ( $\beta$ -HCG) tests at screening (visit 1) and visit 5.

Before	After
Serum <math>\beta</math>-HCG tests will be performed for all female patients who are postmenarchal or <math>\geq</math>12 years of age at screening (visit 1) and visit 5; urine <math>\beta</math>-HCG tests will be performed at all other visits (Table 1).	Serum <math>\beta</math>-HCG tests will be performed for all female patients who are postmenarchal or <math>\geq</math>12 years of age at screening (visit 1) and visit 5; urine <math>\beta</math>-HCG tests will be performed at all <del>other</del> visits (Table 1).

To align Appendix B Study Procedures and Assessments by Visit, with Section 7.4.2.1. (as mentioned above), the discrepancy with pregnancy tests is revised under visit 1 and 5 as shown in the table below.

Before	After

1. Procedures for Screening (Visit 1, Days -28 to -1):
 
 
• serum beta-human chorionic gonadotropin (<math>\beta</math>-HCG) pregnancy test (only female patients who are postmenarchal or <math>\geq 12</math> years of age); inquire and record start / stop date of menstrual period.
 
	
1. Procedures for Screening (Visit 1, Days -28 to -1):
 
 
• serum beta-human chorionic gonadotropin (<math>\beta</math>-HCG) and urine pregnancy tests (only female patients who are postmenarchal or <math>\geq 12</math> years of age); inquire and record start / stop date of menstrual period.
 

4. End of Treatment/Early Withdrawal (Visit 5 [Day 85±3 days]):
 
 
• serum <math>\beta</math>-HCG pregnancy test (only female patients who are postmenarchal or <math>\geq 12</math> years of age); inquire and record start / stop date of menstrual period.
 
	
4. End of Treatment/Early Withdrawal (Visit 5 [Day 85±3 days]):
 
 
• serum <math>\beta</math>-HCG and urine pregnancy tests (only female patients who are postmenarchal or <math>\geq 12</math> years of age); inquire and record start / stop date of menstrual period.
 

To align Section 4.3. Withdrawal Criteria and Procedures for the Patient, with the existing wording in Section 7.9. Assessment of Suicidality, regarding the withdrawal of patients who demonstrate suicidal ideation / behavior from the study, a new bullet point is added in Section 4.3., as shown in the table below.

Before	After

Each patient is free to withdraw from the study or discontinue from IMP at any time, without prejudice to their continued care. Patients must be withdrawn from the study if any of the following events occur:
 
(New bullet added)
	
Each patient is free to withdraw from the study or discontinue from IMP at any time, without prejudice to their continued care. Patients must be withdrawn from the study if any of the following events occur:
 
 
• Any patient who demonstrates suicidal ideation and/or any suicidal behavior at any point during the study should be withdrawn from the study and discontinued from study treatment.
 

These changes will be incorporated into the protocol during the next amendment, as applicable. Please ensure that this letter is maintained with the study protocol. Also, please provide a copy of this letter to your Institutional Review Board/Independent Ethics Committee for review and acknowledgement.

Please feel free to contact [REDACTED] (Tel: [REDACTED]) Cell: [REDACTED]  
[REDACTED] if you have any questions or concerns regarding this  
letter.

Sincerely,

[REDACTED]  
[REDACTED]  
Teva Branded Pharmaceutical Products R&D, Inc.

